4.2.2. Secondary Endpoints

- Phase 1: Objective response rate determined by radiographic disease assessments per mRECIST v1.1.
- Phase 2: Safety and tolerability of the combination as assessed by monitoring the frequency, duration, and severity of AEs, through physical examinations, by evaluating changes in vital signs and ECGs, and through clinical laboratory blood and urine sample evaluations.
- Phases 1 and 2: Durability of response determined by radiographic disease assessment defined as the time from earliest date of disease response until earliest date of disease progression
- Phases 1 and 2: PFS determined from the date of randomization until disease progression or death.
- Phases 1 and 2: The endpoints for assessment of PK of durvalumab and epacadostat include individual durvalumab and epacadostat concentrations and PK parameters.
- Phases 1 and 2: The endpoints for assessment of immunogenicity of durvalumab include the number and percentage of subjects who develop detectable ADAs.

[REDACTED]

- [REDACTED]
- [REDACTED]
- [REDACTED]
- [REDACTED]
- [REDACTED]
- [REDACTED]
- [REDACTED]
- [REDACTED]
- [REDACTED]
- [REDACTED]

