6. STUDY ASSESSMENTS

All study assessments will be performed as indicated in the schedule of assessments (see [Table 24](#)) and laboratory assessments (see [Table 25](#)). The required analytes for each laboratory test are shown in [Table 26](#). The order of assessments is suggested by the order of mention within the schedule of assessments.

Table 24: Schedule of Assessments

Visit (Range)	Screening Days -28 to -1	Treatment Cycles					EOT	Follow-Up	
		C1D1	C1D8	C2D1	Day 1 All Subsequent Cycles	Every 12 Weeks	Discontinuation	Safety Follow-Up Visit 1	Safety Follow-Up Visit 2
		±3 Days	±3 Days	±3 Days	±3 Days	±5 Days	+ 7 Days After Last Dose	42 Days After EOT ±7 Days	90 Days After EOT ±7 Days
Administrative procedures									
Informed consent	X								
Inclusion/exclusion criteria	X	X							
Medical and cancer history	X								
Smoking history	X								
Prior/concomitant medications review	X	X		X	X				
Administer epacadostat at clinic		X	X ^a	X					
Administer durvalumab		X		X	X				
Poststudy anticancer therapy status								X	X
Survival status									
Clinical procedures and assessments									
Comprehensive physical exam	X						X	X	X
Targeted physical exam		X		X	X				
Vital signs and weight (height at screening only)	X	X		X	X		X		
Postinfusion observation ^b		X							
12-lead ECG	X	X ^c		X ^c			X	X	X
Adverse event assessment ^d	X	X		X	X		X	X	X
Laboratory assessments	X	X ^e	X ^f	X	X ^e	X	X	X	X
Chest radiograph	X								
Tumor tissue collection ^g	X			X ^h					
Tumor imaging	X					X ⁱ	X ^j		

C1D1 = Cycle 1 Day 1; C1D8 = Cycle 1 Day 8; C2D1 = Cycle 2 Day 1.

^a **Phase 1 Subjects Only:** Administer epacadostat in clinic on C1D8 when PK assessment is performed.

^b Patients will be observed in clinic for 3 hours after the first infusion of durvalumab is administered.

^c ECGs should be performed on Cycle 1 Day 1 and Cycle 2 Day 1 before epacadostat and durvalumab administration and 1 and 2 hours after administration of epacadostat.

See Table 27 for details regarding specific timing of ECGs.

^d Subjects need to be followed for AEs for 90 days after the last dose of durvalumab or epacadostat (whichever comes later).

^e If LFTs are abnormal, then LFT monitoring should increase to twice per week until resolved to baseline.

^f **Phase 1 Subjects Only:** Pharmacokinetic samples are collected at Cycle 1 Day 8.

^g If subject agrees to such in the ICF, any leftover tissue will be stored for future biomedical research.

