7.6.1. Pharmacokinetics

7.6.1.1. Pharmacokinetic Assessment for Epacadostat

Subject will withhold morning dose of drug during PK days. The time of last dose of study medication and prior meal will be recorded in the CRF. Pharmacokinetic samples will be obtained at the visits indicated in [Table 25](#) and [Table 29](#). After the predose PK sample is drawn (predose is defined as within 24 hours before dosing of durvalumab and before dosing epacadostat), subjects will take epacadostat and then begin infusion of durvalumab. The exact

date and time of the PK blood draws will be recorded in the CRF along with the date and time of the last dose of study drug and last meal preceding the blood draw. Sample collection times for epacadostat are shown in [Table 29](#).

Table 29: Sample Collection Windows for Pharmacokinetic Assessments for Epacadostat

Study Visit	Timing of Sample Relative to Epacadostat Administration						
Cycle 1 Day 1 ^a	Predose ^b	0.5 h ± 10 min	1 h ± 10 min	2 h ± 30 min	4 h ± 30 min	6 h ± 60 min	OPTIONAL 8 to 10 h ± 60 min
Cycle 1 Day 8 ^c	Predose ^b	0.5 h ± 10 min	1 h ± 10 min	2 h ± 30 min	4 h ± 30 min	6 h ± 60 min	OPTIONAL 8 to 10 h ± 60 min
Cycle 2 Day 1 ^a	Predose ^b	0.5 h ± 10 min	1 h ± 10 min	2 h ± 30 min	4 h ± 30 min	6 h ± 60 min	OPTIONAL 8 to 10 h ± 60 min

^a ECGs are also required. See [Table 27](#) for timing of ECGs relative to PK sampling. ECGs should be performed before a PK draw.

^b Predose samples should be collected before durvalumab infusions as well.

^c **Only subjects in Phase 1 should have epacadostat PK performed on Cycle 1 Day 8.**

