7.7.2. Administration of Study Drug

7.7.2.1. Administration of and Compliance With Epacadostat

Subjects will take their dose of epacadostat morning and evening, approximately 12 hours apart without regard to food. Subjects will self-administer epacadostat except on Cycle 1 Day 1, Cycle 1 Day 8 (Phase 1 only), and Cycle 2 Day 1, when the morning dose will be given at the study site clinic.

Epacadostat compliance will be calculated by the sponsor based on the drug accountability documented by the site staff and monitored by the sponsor/designee (tablet counts). The objective is 100% compliance, and investigators and their staff should evaluate compliance at each visit and take appropriate steps to optimize compliance.

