## **2. STUDY INFORMATION, OBJECTIVES, AND ENDPOINTS**

### **2.1. Protocol and Case Report Form Version**

This SAP is based on INCB 24360-203 Protocol Amendment 1 dated 29 SEP 2014 and case report form (CRF) approved on 08 SEP 2014. Unless superseded by an amendment, this SAP will be effective for all subsequent Protocol amendments and CRF versions.

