**Table 9: Sample Collection Windows for Pharmacokinetic Assessments for INCB024360**

Study Visit	Timing of Sample Relative to INCB024360 Administration						
Cycle 1 Day 1	Predose	0.5 h ± 10 min	1 h ± 10 min	2 h ± 30 min	4 h ± 30 min	6 h ± 30 min	OPTIONAL 8 to 10 h ± 30 min
Cycle 1 Day 8	Predose	0.5 h ± 10 min	1 h ± 10 min	2 h ± 30 min	4 h ± 30 min	6 h ± 30 min	OPTIONAL 8 to 10 h ± 30 min
Cycle 2 Day 1	Predose	Anytime (required)					

Measurement of MEDI4736 concentrations in serum will be performed using validated immunoassays. Only subjects who receive at least 1 dose of MEDI4736 and provide at least 1 post-treatment sample will be evaluated. Individual MEDI4736 will be tabulated by dose cohort along with descriptive statistics. The following PK parameters after the first and steady-state dose will be estimated (as data allow): peak concentration ( $C_{max}$ ), trough concentration ( $C_{min}$ ), time to maximum observed concentration ( $t_{max}$ ), and AUC. Accumulation to steady state will be assessed as the ratio of  $C_{max,ss} \cdot C_{max}$  and  $C_{min,ss} \cdot C_{min}$ . All PK parameters will be estimated by noncompartmental analysis. Descriptive statistics of noncompartmental PK parameters will be provided.

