### 7.5.3. INCB024360 Pharmacokinetic Analyses

The noncompartmental analysis for INCB024360 PK will be performed using commercial software such as Phoenix WinNonlin version 6.0 or later (Pharsight Corporation, Mountain View, CA). Nominal times may be used in all cases except when the difference between the actual collection time and the nominal collection time is greater than 15 minutes for samples collected up to 4 hours after administration and greater than 30 minutes for samples collected more than 4 hours after administration. The following 6 PK parameters will be estimated where possible:  $C_{max}$ ,  $T_{max}$ ,  $AUC_{0-t}$ ,  $AUC_{0-12h}$ ,  $t_{1/2}$ , and  $CL/F$  (the latter 3 parameters will only be assessed on C1D8).

For the optional population PK analysis for INCB024360, the data preparation will be performed using SAS version 9.1. [REDACTED]

[REDACTED] Compartment models with first-order absorption and linear elimination will be tested for their ability to characterize the PK of INCB024360. Interindividual variability will be modeled using an exponential error model and explored for each PK parameter. Proportional error, additive error, and mixed additive plus proportional error models will be individually evaluated for their ability to describe the magnitude of residual variability. The first-order conditional estimation method with the interaction option will be used.

After a final base model is identified, covariates will be tested as predictors of PK variability. A generalized additive model analysis will be used as a screening tool to initially identify covariates to be formally tested for statistical significance in NONMEM. The candidate covariates will be incorporated into the PK model as fixed-effect parameters by making the typical values of the structural PK parameters a function of the covariate. NONMEM regression analysis will be performed on the model, with covariate parameters being added in a stepwise univariate fashion during the forward selection process and removed in the model reduction (backward elimination) process. The likelihood ratio test will be used to evaluate the significance of incorporating parameters into or removing parameters from the population model. The accuracy and robustness of the final population PK model will be investigated using a visual predictive check method.

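### The SAP confines noncompartmental AUC0-12h, half-life and CL/F for epacadostat to Cycle 1 Day 8, a Phase 1-only visit in the current protocol, so Phase 2 yields none of the three

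*SAP*

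**What the plan says.** SAP section 7.5.3 names six noncompartmental parameters for epacadostat (INCB024360 in the SAP), in the order Cmax, Tmax, AUC0-t, AUC0-12h, half-life, CL/F, and states that "the latter 3 parameters will only be assessed on C1D8". The three so restricted are AUC0-12h, half-life and CL/F.

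The current protocol limits that visit by phase in three places. The footnote to Table 29 in section 7.6.1.1 reads "Only subjects in Phase 1 should have epacadostat PK performed on Cycle 1 Day 8". In section 6, the Table 24 footnote headed as applying to Phase 1 subjects only says "Pharmacokinetic samples are collected at Cycle 1 Day 8". Section 7.7.2.1 gives the in-clinic dosing days as Cycle 1 Day 1, then "Cycle 1 Day 8 (Phase 1 only), and Cycle 2 Day 1, when the morning dose will be given at the study site clinic".

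Cycle 2 Day 1 carries no phase limit. Protocol Table 29 gives it the same scheme as the other two visits: predose, 0.5, 1, 2, 4 and 6 h, then "OPTIONAL 8 to 10 h ± 60 min". SAP Table 9 shows that visit as predose plus one further sample at any time.

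The secondary endpoint in Protocol section 4.2.2 applies to Phases 1 and 2: "The endpoints for assessment of PK of durvalumab and epacadostat include individual durvalumab and epacadostat concentrations and PK parameters". SAP section 2.1 says the SAP is based on Protocol Amendment 1 and adds: "Unless superseded by an amendment, this SAP will be effective for all subsequent Protocol amendments and CRF versions". SAP Table 15 lists only the original version, dated 26 NOV 2014.

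**The concern.** The SAP rule and the current sampling schedule no longer fit together. The only visit at which the SAP permits three of the six parameters is one that Phase 2 subjects do not have, while the visit at which both phases now have a full profile is not named for them. PK parameters are a secondary endpoint in both phases, and the protocol synopsis gives half-life, AUC and clearance as examples of what will be determined for each drug.

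At stake is the precision of full-interval exposure, half-life and apparent clearance of epacadostat given with durvalumab at 100 and 300 mg BID. The primary response analysis and the safety analyses are not affected.

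**Working it through.** The plan states no figure to reproduce on this point. The check sets the passages side by side and then counts.

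**1. Which visits can supply the three parameters**

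| Visit | Protocol Table 29 sampling | Phases sampled | SAP Table 9 sampling | AUC0-12h, half-life, CL/F under SAP 7.5.3 |
|---|---|---|---|---|
| C1D1 | 6 required + 1 optional | 1 and 2 | 6 required + 1 optional | No |
| C1D8 | 6 required + 1 optional | 1 only | 6 required + 1 optional | Yes |
| C2D1 | 6 required + 1 optional | 1 and 2 | 2 | No |

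Phase 2 visits with both a profile and permission: 0.

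**2. Whether C2D1 is suitable**

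Cycles last 14 days, so C2D1 is nominally Day 15. Protocol section 1.1.13.2 treats Cycle 1 Day 15 as steady state in the monotherapy study. Section 1.1.13.1 gives an effective half-life of 4 to 6 h; 14 × 24 / 6 = 56 half-lives, so with uninterrupted dosing steady state is not in doubt.

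**3. How many subjects contribute**

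- Phase 1: up to 36 subjects over 6 dose levels (Protocol section 9.2.1), 36 / 6 = 6 per dose level. Replacement of subjects not evaluable for dose-limiting toxicity could add a few.
- Phase 2 expansion cohorts (Protocol Table 6): 8 + 7 + 4 = 19 at 100 mg BID; 3 × 28 = 84 at 300 mg BID.
- The melanoma, TNBC and gastric cohorts add 15 + 13 + 9 = 37 (Stage 1 only) to 40 + 29 + 20 = 89. Their dose is not fixed in the tables, so they are left out of the per-dose counts.
- Check on the totals: 37 + 103 = 140 and 89 + 103 = 192, the protocol's stated range.
- Share of all planned subjects who could contribute under the present rule: 36 / (36 + 192) = 15.8% to 36 / (36 + 140) = 20.5%.

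**4. Allowance for unusable profiles**

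The documents give no attrition figure before C2D1. The footnote to Protocol Table 3 says half-life, and hence AUC0-12h, could not be estimated for 4 subjects in the monotherapy study. The table's group sizes sum to 3 + 4 + 5 + 5 + 8 + 5 + 12 + 4 = 46, so 4 / 46 = 8.7%. Applying that rate gives 84 × 42 / 46 ≈ 77 and 19 × 42 / 46 ≈ 17. If only half were usable (an assumption), 84 / 2 = 42 and 19 / 2 ≈ 9 would remain.

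**5. What this does to precision (illustration)**

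Assume log-normal CL/F with the monotherapy CVs in Protocol Table 3: 20.9 / 45.8 = 45.6% at 100 mg BID and 6.19 / 70.4 = 8.8% at 300 mg BID, each from 5 subjects. The 95% interval for the geometric mean is the estimate multiplied and divided by exp(t × s / √n), with s = √ln(1 + CV²).

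- 100 mg BID, s = 0.435. For n = 6, t = 2.571: factor 1.58. For n = 6 + 19 = 25, t = 2.064: factor 1.20.
- 300 mg BID. The 8.8% CV is low beside the other doses, so a range of 8.8% to 45.6% is used. For n = 6: factor 1.10 to 1.58. For n = 6 + 84 = 90, t = 1.987: factor 1.02 to 1.10.

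**The case against.** The strongest reply has four parts.

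*The rule was sensible when written.* In the SAP's own schedule, C1D8 was the only full profile after the first dose and epacadostat sampling on that day was not limited to Phase 1; two samples at C2D1 could not support these parameters. This stands: the gap is a failure to update the SAP, not a poor choice of method. The Amendment 4 entry in the change log says PK timing was revised to gain information at predose, peak and steady state. The SAP says it governs later amendments, so the old rule still applies.

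*The Phase 2 profiles are not wasted.* A reader might infer that the C2D1 samples would go unused, that Phase 2 would have no steady-state exposure estimate, or that the secondary endpoint would be empty there. The documents do not support this. Section 7.5.3 puts no visit limit on Cmax, Tmax or AUC0-t, SAP section 7.5.5 has observed concentrations listed, and the endpoint does not name the three restricted parameters. What is missing is narrower. AUC0-t is only a partial substitute: its end time can depend on whether the optional late sample was drawn, and it gives neither half-life nor clearance.

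*Population PK could supply clearance in Phase 2.* SAP section 7.5 allows it alongside or instead of noncompartmental analysis. This also stands, but section 7.5.3 describes it as optional, so it is not a committed source. Part of that text is redacted, so its intended data scope cannot be judged.

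*Enrolment is not evaluable profiles.* Correct. Dose holds, early discontinuation and missed samples will reduce the numbers, and required sampling stops at 6 h. For that reason 140 to 192 should not be read as the number of profiles lost.

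**Conclusion.** The point holds as a SAP/protocol inconsistency with a limited consequence. Under the rule as written, the noncompartmental analysis gives no AUC0-12h, half-life or CL/F for any Phase 2 subject. At 100 and 300 mg BID these would come from about 6 planned Phase 1 subjects per dose level at most, although 19 and 84 Phase 2 subjects are planned at those doses in the expansion cohorts. Even if only half of the latter gave usable profiles, the additional contributors would outnumber Phase 1 at both doses.

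This rests on three assumptions: that the original SAP remains in force, as its own section 2.1 and Table 15 indicate; that Protocol Table 29 is followed in Phase 2; and that population PK is not made mandatory elsewhere. The precision figures borrow monotherapy variability from groups of 5 and are illustrative only. Severity is low: it is a worthwhile improvement to a secondary endpoint, with no bearing on the primary conclusion.

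**What to change.** Amend the SAP in two places.

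1. Replace the C2D1 row of SAP Table 9 with the Protocol Table 29 scheme, and mark C1D8 as Phase 1 only.
2. In section 7.5.3, derive AUC0-12h, half-life and CL/F, where estimable, on C2D1 in both phases and on C1D8 in Phase 1. Report by dose how many subjects had an estimable value.

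If the sponsor means Phase 2 clearance to come from population PK instead, the SAP should say so and make that analysis mandatory.

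The cost is SAP wording and some programming. The samples are already required by the protocol, so there are no added visits, draws or subject burden.

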### 7.5.4. Immunogenicity for MEDI4736

Validated assays will be used for the determination of ADAs to MEDI4736 in human serum.

Only subjects who receive at least 1 dose of MEDI4736 and provide at least 1 post-treatment sample will be evaluated. Immunogenicity results will be analyzed descriptively by summarizing the number and percentage of subjects who develop detectable anti-MEDI4736 antibodies. Samples confirmed positive may also be evaluated for neutralizing antibody activity.

### 7.5.5. Report

A PK report will be prepared to include listings of observed INCB024360 plasma concentration data and estimated PK parameters in accordance with guidance of both US and EU regulatory authorities.

## 8. SAFETY AND TOLERABILITY

Sample data displays are provided in [Appendix C](#).

### 8.1. General Considerations

The analyses for this section will be provided for Phase 1 and 2 portion using Phase 1 and Phase 2 safety evaluable population, respectively. Summary tables may be replaced with listings when appropriate. For instance, an AE frequency table may be replaced with a listing if it only contains a few unique preferred terms reported on relatively few subjects. Additional summaries for specific subgroups may be included on an ad hoc basis.

### 8.2. Adverse Events

#### 8.2.1. Adverse Event Definitions

A treatment-emergent adverse event (TEAE) is any AE either reported for the first time or worsening of a pre-existing event after first dose of study drug. Analysis of AEs (as discussed below) will be limited to TEAEs, but data listings will include all AEs regardless of their timing to study drug administration.

Adverse Events will be tabulated by the MedDRA preferred term and system organ class. Severity of AEs will be described and graded using the National Cancer Institute Common Terminology Criteria for Adverse Events (CTCAE) v4.03. The CTCAE reporting guidelines and grading details are available on the Cancer Therapy Evaluation Program website.

A grading (severity) scale is provided for each AE term. If the toxicity is not included in the CTCAE v4.03 criteria, it will be rated on a scale of 1 to 4 as follows: 1 = mild, 2 = moderate, 3 = severe, and 4 = life threatening. All toxicities will be graded based on the worst level reached, not the level they may have reached if they had not been treated. When the intensity of

an AE changes over time for a reporting period (eg, between visits), each change in intensity will be reported as an AE until the event resolves.

The subset of AEs considered by the investigator to be related to INCB024360 or MEDI4736 will be considered to be treatment-related AEs. If the investigator does not specify the relationship of the AE to study drug, the AE will be considered to be treatment related. The incidence of AEs and treatment-related AEs will be tabulated. Serious adverse events (SAEs) will also be tabulated.

Any missing onset date, causality, or severity must be queried for resolution. Unsolved missing values will be handled according to the following rules:

- An unsolved missing causality will be considered treatment related.
- An unsolved missing severity will be identified as an unknown severity.

For purposes of analysis, all AEs will be considered TEAEs unless the AE can unequivocally be defined as not treatment emergent. Therefore, an unsolved missing onset date will be considered treatment emergent, with the following exceptions:

- If the stop/resolution date is before the first dose administration date on Day 1, then the AE will be considered as not being treatment emergent.
- If both the month and day are missing, and the last day of the year is before the first dose administration date on Day 1, then the AE will not be considered treatment emergent.
- If only the day is missing, and the last day of the month is before the first dose administration date on Day 1, then the AE will not be considered treatment emergent.
- If only the day is missing, and the first day of the month is after the first dose administration date on Day 1, then the AE will be considered treatment emergent.

### **8.2.2. Adverse Event Summaries**

An overall summary of AEs by treatment group will include:

- Number (%) of subjects reporting any TEAEs
- Number (%) of subjects reporting any treatment-related TEAEs
- Number (%) of subjects reporting any SAEs
- Number (%) of subjects reporting any Grade 3 or 4 TEAEs
- Number (%) of subjects who temporarily interrupted study drug because of TEAEs
- Number (%) of subjects who permanently discontinued study drug because of TEAEs
- Number (%) of subjects who withdrew from study because of a TEAE
- Number (%) of subjects with INCB024360 dose reductions because of TEAEs
- Number (%) of subjects who had a fatal TEAE

The following summaries will be produced by MedDRA term (if  $\leq 10$  subjects appear in a table, a listing may be appropriate):

- Number (%) of subjects reporting TEAEs by system organ class and preferred term
- Number (%) of subjects reporting TEAEs by preferred term in decreasing order of frequency
- Number (%) of subjects reporting TEAEs by system organ class, preferred term, and highest CTCAE grade
- Number (%) of subjects reporting any Grade 3 or 4 TEAEs by system organ class and preferred term
- Number (%) of subjects reporting treatment-related AEs by system organ class and preferred term
- Number (%) of subjects reporting treatment-related AEs by preferred term in decreasing order of frequency
- Number (%) of subjects reporting treatment-related AEs by system organ class, preferred term, and highest CTCAE grade
- Number (%) of subjects reporting any Grade 3 or 4 treatment-related AEs by system organ class and preferred term
- Number (%) of subjects reporting TEAEs leading to death by system organ class and preferred term
- Number (%) of subjects reporting treatment emergent SAEs by system organ class and preferred term
- Number (%) of subjects reporting treatment-related SAEs by system organ class and preferred term
- Number (%) of subjects reporting TEAEs leading to withdrawal from the study by system organ class and preferred term
- Number (%) of subjects reporting TEAEs leading to dose reduction of INCB024360 by system organ class and preferred term
- Number (%) of subjects reporting TEAEs leading to discontinuation of medication by system organ class and preferred term
- Number (%) of subjects reporting TEAEs requiring concomitant medications by system organ class and preferred term
- Number (%) of subjects reporting treatment-emergent non-SAE by system organ class and preferred term
- Number (%) of subjects reporting events of special interest by system organ class and preferred term
- Number (%) of subjects reporting treatment-emergent immune-related AEs by system organ class and preferred term
- Number (%) of subjects reporting Grade 3 or higher treatment-emergent immune-related AEs by system organ class and preferred term

For the last 2 items above, Table 10 includes the full list of preferred terms that should be considered as the immune-related AEs. Pneumonitis, hypersensitivity reactions, hepatic function abnormalities (hepatotoxicity), and serotonin syndrome should be considered as the events of special interest.

